### 4.3. Analysis of the working hypothesis:

Each hormonal determination of each day of stimulation in which it is determined will be compared by means of Student "t" for independent samples, once the normal distribution of the values by means of the tests of Kolmogorov-Smirnov and Shapiro-Wilks has been verified. Otherwise, comparisons will be made with the Mann-Whitney test. The area under the curve during ovarian stimulation will be calculated for each of the hormones included in the study, and both groups will be compared equally. The proportion of patients with elevated Progesterone on the last day of stimulation ( $>1.5 \text{ ng/mL}$ ) will

be compared between both groups by Chi-square test. For this particular event the relative risk and its 95% confidence interval will also be calculated.

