## Protocol Synopsis

---

Protocol Title: Follicular Esteroidogenesis in Controlled Ovarian Stimulation

---

EudraCT Code: 2015-005762-28

---

Sponsor's protocol version and date: 1.0 of 12/1/2015

---

Sponsor:

IVI Valencia

[name]

[contact]

[[name] / [name]]

---

Principal Investigator:

[name]

Instituto Valenciano de Infertilidad

[contact]

[name]/[name]

---

Phase: Fase IV

---

Centros participantes:

IVI Valencia

---

Investigational Medicinal Product (IMP): Recombinant FSH, Highly Purified HMG, Ganirelix, Triptorelin

---

Primary Objective: To compare the serum concentrations of the different hormones involved in follicular steroidogenesis during an EOC cycle between FSHr and hpHMG.

---

Secundary Objectives:

- Define the area under the curve for each of the follicular steroids along the EOC in cycles stimulated with FSHr and hpHMG.
- Calculate the contribution to the circulation of each of the follicular steroids per unit of follicular volume.
- To identify the metabolic pathways of follicular steroidogenesis as a function of the type of gonadotrophin used for COC.
- To compare the concentration of steroids in follicular liquid in stimulated cycles with FSHr and hpHMG.
- Correlate the hormone levels observed in serum with the concentration in follicular fluid]

---

Methodology: 110 women will be included (55 in each study group, i) FSHr; ii) hpHMG) with normal ovarian function, who will follow ovarian stimulation in cycle with GnRH Antagonists. For greater uniformity in the study population, oocyte donors will be used.

Serum extractions and transvaginal ultrasound for folliculometry will be performed on the days of stimulation 1, 4, 6, 8 and the day of administration of the triptorelin. In the follicular puncture for the extraction of the oocytes, the first follicle will be individually aspirated to obtain the follicular fluid. The samples obtained will be frozen and stored at -80°C for later analysis.

In each serum sample they will be determined: Pregnenolone, Progesterone, 17-OH-Progesterone, Dehydroepiandrosterone, Androstenodione, Testosterone, Estrone and Estradiol.

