Each day's hormone concentration will be compared between the two groups, so that the profile of each of the hormones can be defined for both stimulation protocols, and thus the follicular steroidogenesis profile. The area under the curve during ovarian stimulation will be calculated for each of the hormones included in the study, and both groups will be compared. The proportion of patients with elevated Progesterone on the last day of stimulation ( $>1.5$  ng/mL) will be compared between both groups.

Follicular fluid concentrations will be defined for each of the steroids analyzed, and the values between both groups will be compared, as well as their correlation with the levels observed in serum.

Clinical Trial Prospective randomized, open, parallel groups.

---

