**Exclusion criteria:**

- Kidney failure
- Polycystic ovary
- BMI  $\geq 25.0$
- Any systemic or metabolic disorder that contraindicates the use of gonadotrophins.
- Any reason for exclusion from the oocyte donation program.

Test Product, Dose and Mode of Administration:

Arm 1:

*MEDICATION: Recombinant FSH*

*Therapeutic group: Gonadotrophins for ovarian stimulation*

*Route of administration: subcutaneous*

*Dose: 225 IU/day*

Arm 2:

*MEDICATION: Highly purified HMG*

*Therapeutic group: Gonadotrophins for ovarian stimulation*

*Route of administration: subcutaneous*

*Dose: 225 IU/day*

Reference Therapy, dose and Mode of administration:

---

Duration of study:

- Recruitment period: April 2016-July 2016
- Estimated end-of-treatment date of the last patient: October 2016
- End of study date: December 2016

---

Schedule of Assessments:

The patients will be recruited from the population of oocyte donors of the IVI Valencia programme. Patients will come to the clinic on their 2nd day of menstruation of the cycle in which ovarian stimulation is to be performed. At that time patients will be randomly assigned 1:1 to start COCs with 225 IU/day of FSHr (Gonal F) or hpHMG (Menopur). On the 6th day of stimulation, all patients will start a daily dose of 0.25 mg of the antagonist (Orgalutran), until the day of the final induction of oocyatic maturation. When at least 8 follicles reach a diameter of at least 17 mm, a bolus of 0.2 mg of triptorelin (Decapeptyl) should be administered. Follicular puncture will be performed 36 hours later, according to usual clinical practice.

Serum extractions and transvaginal ultrasound for folliculometry will be performed on the days of stimulation 1, 4, 6, 8 and the day of administration of the triptorelin, and the follicular liquid of the first aspirated follicle will be individually aspirated. The samples obtained will be frozen and stored at -80°C for later analysis.

Each serum sample shall be determined:

- Pregnenolone
- Progesterone
- 17-OH-Progesterone
- Dehydroepiandrostenodiona
- Androstenodione
- Testosterone
- Estrona
- Estradiol
- FSH
- LH

---

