### 3. Study Variables and Database

#### 3.1. Main variable:

Area under the serum progesterone curve during ovarian stimulation

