#### 3.2. Secondary variables:

- Area under the serum estradiol curve during ovarian stimulation
- Area under the serum Pregnenolone curve during ovarian stimulation
- Area under the 17-OH serum progesterone curve during ovarian stimulation
- Area under the serum Androstenodione curve during ovarian stimulation
- Area under the serum Dehydroandrostenedione curve during ovarian stimulation
- Area under the serum Testosterone curve during ovarian stimulation
- Area under the curve of Serum Estrone during ovarian stimulation
- Area under the serum FSH curve during ovarian stimulation
- Area under the serum LH curve during ovarian stimulation
- Concentration of P in follicular liquid
- Concentration of Estradiol in follicular liquid
- Concentration of Pregnenolone in follicular liquid
- Concentration of 17-OH Progesterone in follicular liquid
- Concentration of Androstenodione in follicular liquid
- Concentration of Dehydroepiandrostenodione in follicular liquid
- Concentration of Testosterone in follicular liquid
- Concentration of Estrone in follicular liquid

- Concentration of FSH in follicular liquid
- Concentration of LH in follicular liquid

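### Section 4.3 does not carry through the main-variable ranking: it compares every serum hormone on every sampling day under the working hypothesis, with no multiplicity control and no descriptive label

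*Combined protocol and SAP*

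**What the plan says.** Section 3.1 gives a single main variable: "Area under the serum progesterone curve during ovarian stimulation". Section 3.2 lists nine other serum AUCs, among them "Area under the serum LH curve during ovarian stimulation", and ten follicular-fluid concentrations. No single-day serum value appears in any list in section 3, and neither does the proportion of women with progesterone above 1.5 ng/mL.

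Section 4.3 then sets out three things: "Each hormonal determination of each day of stimulation in which it is determined will be compared by means of Student" t test, with Mann-Whitney as the fallback; AUCs calculated and compared for every hormone, with progesterone not singled out; and a chi-square test of the 1.5 ng/mL proportion. It gives no significance level, testing order or multiplicity rule, and calls nothing exploratory.

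Three other places bear on which result decides:

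- Protocol Synopsis, Primary Objective: "To compare the serum concentrations of the different hormones involved in follicular steroidogenesis during an EOC cycle between FSHr and hpHMG".
- Protocol Synopsis, Methodology: the daily comparisons are made "so that the profile of each of the hormones can be defined for both stimulation protocols".
- Section 2, Sample size: the calculation uses progesterone on the last day of stimulation, at 5% alpha and 80% power.

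On timing, the Schedule of Assessments in the synopsis has women attend on day 2 of menstruation, and "At that time patients will be randomly assigned 1:1 to start COCs". Serum is drawn on stimulation days 1, 4, 6 and 8 and on the triptorelin day.

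**The concern.** The section that should say how the main variable is analysed and what status it has does neither. The daily tests, which section 3 ranks nowhere, come under the working-hypothesis heading, and they match the multi-hormone wording of the primary objective more closely than one progesterone AUC does. A report that follows 4.3 could present a handful of nominally significant hormone-days as a difference in steroidogenesis between FSHr and hpHMG, and so as the objective met, whatever the progesterone AUC showed. Correlation makes this more awkward: when hormones and days move together, chance findings come in clusters, and a cluster can look like a pathway effect.

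Day 1 is a further oddity. Randomisation takes place at the visit where stimulation begins. If the day-1 blood is drawn before the first dose, those comparisons cannot show a treatment effect.

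**Working it through.** **The plan's own figure.** Inputs from section 2: means 0.73 and 0.99, SDs 0.42 and 0.48, alpha 5%, power 80%.

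- Difference: 0.99 − 0.73 = 0.26. Root-mean-square SD: √((0.42² + 0.48²)/2) = 0.451.
- n per group = 2 × (1.960 + 0.842)² × 0.451² / 0.26² = 47.2, so 48, as stated. A one-sided 5% would give 38, so the plan's 5% is two-sided. It applies to one comparison, last-day progesterone.

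**Number of daily comparisons.** There are five sampling days (1, 4, 6, 8, triptorelin day). The synopsis Methodology names 8 hormones: "In each serum sample they will be determined: Pregnenolone, Progesterone, 17-OH-Progesterone, Dehydroepiandrosterone, Androstenodione, Testosterone, Estrone and Estradiol". The Schedule of Assessments and section 3.2 add FSH and LH, making 10.

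- 10 × 5 = 50
- 8 × 5 = 40
- 8 steroids × 4 days after day 1 = 32

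The last set is the one most likely to be read against the primary objective, since FSH and LH are not follicular steroids and a pre-dose day 1 cannot show an effect. The triptorelin day is set by response ("When at least 8 follicles reach a diameter of at least 17 mm"), so it may coincide with day 8 for some women; the two time points would then overlap.

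**Expected false positives at 5% if no hormone differs** (this does not depend on correlation):

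- 32 × 0.05 = 1.6
- 40 × 0.05 = 2.0
- 50 × 0.05 = 2.5

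**Chance of at least one.** Under independence, 1 − 0.95^m. Otherwise by simulation of correlated normal test statistics (200,000 draws, two-sided 5%). The correlations are assumptions, written as within a hormone across days / between hormones.

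| Assumption | 32 tests | 40 tests | 50 tests |
|---|---|---|---|
| Independent (upper bound) | 81% | 87% | 92% |
| Moderate: 0.5/0.2 to 0.7/0.4 | about 70 to 55% | 76 to 59% | 83 to 66% |
| Strong: 0.8/0.6 to 0.9/0.7 | about 40 to 30% | 43 to 32% | 47 to 35% |
| 0.9 everywhere | about 17% | 18% | 19% |

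Under strong correlation the median count in the 50-test set is 0, but when any false positive occurs the average is 5 to 7. That is the clustering described above.

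**The main test.** One test of the progesterone AUC at 5% has a 5% error rate, however many other tests are run, provided only that test decides.

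**The case against.** The strongest reply is that the ranking already exists. Sections 3 and 4 belong to the same short plan; a main variable named in 3.1 need not be renamed in 4.3 to keep its status, and the order of sentences in 4.3 is not a testing hierarchy. The synopsis also gives the daily comparisons a profile-defining purpose. This has force. A reader might infer that the plan leaves entirely open which result decides, or that its primary error rate is near 90%. The documents support neither: 3.1 implies the answer, and the progesterone AUC test is not inflated. What survives is that 4.3 does not say so, while the primary objective and the sample size each point elsewhere.

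Four narrower replies also stand in part:

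- Section 4.3 states no alpha. The only 5% in the documents is in the sample-size text, so testing at an unadjusted 5% is the natural inference but not something the plan prescribes.
- The counts of 40 and 50 include comparisons that few would read as follicular steroidogenesis under treatment, which is why the 32-test figures are given.
- The calculation supposes that no hormone differs, whereas the plan expects progesterone to differ. Without progesterone, 7 × 4 = 28 steroid tests remain after day 1, with 28 × 0.05 = 1.4 false positives expected.
- One might say the day-1 tests merely repeat section 4.2. That section speaks only of baseline and demographic characteristics and names no hormone, so the overlap is not established.

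**Conclusion.** The concern holds as a gap between sections, not as an inflated primary test. Section 4.3 should carry the ranking of section 3 and does not, and the breadth of the primary objective makes the omission matter.

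If no hormone differs, 1.6 to 2.5 nominally significant daily results are expected. For the 8 steroids after day 1, the chance of at least one is at most 81% and about 17 to 70% under the assumed correlations. These figures rest on three things: an inferred 5% level, the global null, and correlations the documents do not supply. They show that chance findings are a real possibility, but do not give the trial's actual error rate. The day-1 point is conditional on the sample preceding the first dose, which the documents do not state.

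**What to change.** 1. State in 4.3 that the progesterone AUC is the single confirmatory test, at two-sided 5%, and word the primary objective to match.
2. Report the daily values as profile description, the purpose the synopsis gives them, with confidence intervals. Label the other AUCs, the follicular-fluid concentrations, last-day progesterone and the proportion above 1.5 ng/mL as secondary or exploratory, and say they are not to be read as meeting the primary objective.
3. Take day 1 out of the hypothesis tests. State whether that sample precedes the first dose; if it does, use it as the baseline covariate in the AUC comparison.

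The cost is a few sentences in section 4.3, section 3.2 and the primary objective. It needs no new data, and at most a covariate-adjusted model for the AUC. The downside is that some nominally significant secondary results can no longer be presented as confirmatory.

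No correction across hormone-days is asked for. With 48 per group and the plan's progesterone effect, Bonferroni over 40 or 50 tests would leave power of about 34% or 32%. Holm or Benjamini-Hochberg across the secondary AUCs, or a repeated-measures model for the daily values, are options for the sponsor and not part of this point.

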### 2. Sample size

A previous study conducted by our group (Bosch et al, 2008) in which these two same protocols were compared in terms of clinical outcomes, showed that the serum P on the last day of stimulation was  $0.73 \pm 0.42$  in the HMG group vs  $0.99 \pm 0.48$  in the FSH group ( $p<0.001$ ). According to these data, to determine a difference of this magnitude with a 95% confidence level (5% alpha error) and 80% power (20% beta error), 48 patients per group are required. Assuming a loss rate of 15%, 55 patients should be randomly assigned to each group, i.e. 110 patients in total.

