### 4.1. Descriptive data analysis:

Description of continuous quantitative variables (all study variables are) in their central parameters (mean and median) and dispersion values (standard deviation, p10, p25, p75, p90, maximum and minimum).

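### Section 4.3 compares the progesterone AUC by an unadjusted test, with no named effect estimate or confidence interval, and leaves the day-1 progesterone value unused as a covariate

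*Combined protocol and SAP*

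**What the plan says.** Section 3.1 names the main variable: "Area under the serum progesterone curve during ovarian stimulation".

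Section 4.3 sets out the comparison. The default for single days is the two-sample t-test: "Each hormonal determination of each day of stimulation in which it is determined will be compared by means of Student". It is conditional on a check of the distribution, to be used only "once the normal distribution of the values by means of the tests of Kolmogorov-Smirnov and Shapiro-Wilks has been verified". If that check fails, a rank test takes its place: "Otherwise, comparisons will be made with the Mann-Whitney test". As for the AUCs, they are to be "calculated for each of the hormones included in the study, and both groups will be compared equally", which I read as the same rule.

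The only between-arm estimate with an interval belongs to the proportion with last-day progesterone above 1.5 ng/mL: "For this particular event the relative risk and its 95% confidence interval will also be calculated". Section 4.1 plans summaries: "Description of continuous quantitative variables (all study variables are) in their central parameters (mean and median) and dispersion values". It does not say whether these are given by arm, and it plans no contrast between arms.

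The Schedule of Assessments in the synopsis places serum draws on stimulation days 1, 4, 6 and 8 and on the triptorelin day. It does not say whether the day-1 sample comes before the first gonadotrophin injection. No adjusted model appears anywhere, and the control variables of section 3.3 are tied to no analysis.

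**The concern.** The trial sets out to compare hormone concentrations between two gonadotrophins, so the size of the difference is the result of interest. As written, the main analysis promises a test but no stated quantity. If the normality tests point to Mann-Whitney, the planned result is a rank-test p value. The investigators would then choose a mean difference, a median difference, a location shift or a ratio after seeing the data.

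The day-1 progesterone value is also collected but not used to explain variation between women. If it is a true baseline, adjusting for it is a gain in precision from data already in hand.

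**Working it through.** **1. The plan's own figure.** Section 2 (Sample size) uses last-day serum progesterone: 0.73 ± 0.42 (HMG) and 0.99 ± 0.48 (FSH), 5% alpha, 80% power, 48 per group.
- Difference: 0.99 − 0.73 = 0.26.
- Pooled SD: √((0.42² + 0.48²)/2) = 0.451.
- n per group, two-sided: 2 × (0.451 × (1.96 + 0.842)/0.26)² = 47.2, rounded up to 48.

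The stated 48 reproduces. Power by the exact t distribution at 48 per arm is 0.798.

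**2. What adjustment does.** In an ANCOVA, residual variance is multiplied by 1 − r² and interval width by √(1 − r²). The documents give no r, so these values are assumed.

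| r | Variance reduction | Interval width factor |
|---|---|---|
| 0.1 | 1% | 0.995 |
| 0.2 | 4% | 0.980 |
| 0.3 | 9% | 0.954 |
| 0.5 | 25% | 0.866 |

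**3. How much r could be built in.** Assume the AUC is computed by trapezoids over days 1, 4, 6, 8 and trigger day T. The weights are 1.5, 2.5, 2, (T−6)/2 and (T−8)/2, so day 1 is itself part of the outcome. T = 9 to 12 is assumed.
- Days uncorrelated, equal SDs: r = 1.5/√(sum of squared weights). At T = 10 this is 1.5/√17.5 = 0.36; the range is 0.30–0.39.
- Day-1 SD half of the later SDs: 0.15–0.21.
- Day-1 SD a quarter of the later SDs: 0.08–0.10.
- SDs rising 0.25, 0.4, 0.6, 0.8, 1: 0.11–0.18.
- Days correlated at an assumed 0.3, day-1 SD equal to or half of the later SDs: 0.52–0.63.

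The purely built-in part may therefore be small. Values above 0.5 need a between-day correlation that the documents do not report.

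**4. Proxy for power.** The documents give no SD for the AUC, so its power cannot be computed. As an illustration only, take last-day progesterone on the raw scale with 48 per arm. The noncentrality is 0.26/(0.451 × √(1 − r²) × √(2/48)), with 94 degrees of freedom unadjusted and 93 adjusted.

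| r (assumed) | Noncentrality | Power |
|---|---|---|
| 0 (unadjusted) | 2.82 | 0.80 |
| 0.2 | 2.88 | 0.81 |
| 0.3 | 2.96 | 0.83 |
| 0.5 | 3.26 | 0.90 |

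Last-day progesterone has no built-in correlation with day 1, so the r values of step 3 should not be paired with these powers.

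**5. Why a log scale is reasonable.** Normal distributions with the section 2 means and SDs would put Φ(−0.73/0.42) = 4.1% and Φ(−0.99/0.48) = 2.0% of concentrations below zero, which suggests right skew. Matching lognormals have log SDs √ln(1 + (0.42/0.73)²) = 0.535 and √ln(1 + (0.48/0.99)²) = 0.459, pooled 0.499. The ratio of geometric means is exp(0.342) = 1.41. This concerns last-day values and does not establish the distribution of the AUC.

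**6. Does the test-choice rule do harm?** This was simulated with 10,000 runs, 48 per arm and section 2 inputs, assuming that Shapiro-Wilk p < 0.05 in either arm sends the trial to Mann-Whitney.
- Lognormal values: type I error 4.9%, power 0.90, against 0.80 for a fixed raw t-test and 0.91 for an unadjusted log t-test. Mann-Whitney is chosen in 99% of trials.
- Normal values: type I error 5.5%, against 5.3% for the t-test alone in the same runs. Power is 0.80, and Mann-Whitney is chosen in 10% of trials.

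No material loss appears. The switching rates are for last-day values. For a trapezoid AUC of lognormal days (trigger day 10, same CV each day, assumed), Mann-Whitney was chosen in 71%, 88% and 96% of trials at between-day correlations of 0, 0.3 and 0.6.

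**The case against.** The strongest reply is that nothing in the planned test is wrong. Randomisation makes the unadjusted comparison valid, and the rule keeps its error rate and power (step 6). A reader might infer that letting normality tests pick the test undermines the primary result; the simulation does not support that. This part of the reply stands in full.

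Second, section 4.1 plans means, medians and SDs. If these are reported by arm, a mean difference and its interval can be worked out from them. This stands in part: a reader could derive an estimate, but the plan does not commit to one. Strictly, too, section 4.3 has the normality tests choose a test and names no effect measure under either branch, so a switch of measure is an inference from the choice of test.

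Third, the covariate gain rests on unknowns: r, and whether the day-1 sample is pre-dose. This stands. A reader might take a correlation above 0.5 as guaranteed because day 1 is part of the AUC, or take the powers in step 4 as powers for the AUC. The documents support neither reading.

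Finally, the log scale is a reasonable choice, but the documents do not force it.

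**Conclusion.** The point holds as an improvement to make; the planned test is not invalid. Section 4.3 fixes no effect estimate or interval for the main variable and leaves a sampled day-1 value unused.

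The first gap is certain from the text. The second costs precision only if the day-1 sample is pre-dose, by a factor 1 − r² in variance: 1–4% at r = 0.1–0.2, 9% at 0.3 and 25% at 0.5, all assumed. If r is small the gain is negligible. The gain in power for the AUC cannot be computed from the documents; the proxy shows 0.80 rising to between 0.81 and 0.90 for r between 0.2 and 0.5.

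A separate minor matter, with no bearing on the primary result: section 4.2 uses Levene's test to check normality, but that test checks equality of variances.

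**What to change.** In section 4.3, pre-specify as primary one ANCOVA of progesterone AUC on arm and day-1 progesterone, and report one adjusted effect with its 95% CI. If AUC and covariate are log-transformed, which is reasonable for positive and apparently skewed concentrations, the effect is the geometric mean ratio.

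First confirm, and state in the plan, that the day-1 sample is drawn before the first gonadotrophin dose. If it is not, use the same model without the covariate; the fixed estimate and interval are still gained. Keep Mann-Whitney as a sensitivity analysis. In section 4.2, do not cite Levene's test as a check of normality.

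The cost is a few sentences and a little more analysis work, with no new samples, visits or participants.
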